Acute Treatment Phase. After randomization, and on the first day of each block of treatment, the administrator will determine the motor threshold (MT). The administrator will then deliver left prefrontal active rTMS treatment or Sham (Control) rTMS treatment for 20 to 30 sessions in blocks of 5 sessions. Patients are first tested for “remission” after the first 20 sessions of treatment and then again at the 25th and 30th sessions. “Remission” is defined as a decrease in Hamilton Rating Scale for Depression to 10 or less. **Patients will be retested for remission following the last treatment in each 5-session block.**

- If a participant remits after the first 20 sessions, the participant will enter the 24 week follow-up phase; all participants will receive a minimum of 20 treatments before being evaluated for remission;
- If a participant does not remit after the first 20 sessions of treatment, the participant will be offered an additional 5 or 10 sessions of treatment and retested for “remission” after 25 or 30 sessions. This procedure may continue for a maximum of 30 sessions total treatment.
- If the participant remits, he/she will enter the 24 week follow-up phase during which they will receive a “taper” of treatments over three weeks. The taper will include 3 treatment sessions in the first week, 2 in the second week and 1 in the last week of the taper;
- If a participant does not remit at the end of 30 sessions of treatment or drops out during treatment, the participant will be considered a treatment “failure” for the purpose of the primary analyses. The participant will enter the 24 week follow-up phase. Patients who are treatment “failures” will not receive a “taper” of treatments.

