Units of 5 sessions will normally be delivered over one week’s time. As is the case with other somatic treatments such as electroconvulsive therapy, some consideration of scheduling flexibility must be made to accommodate holidays and other events. These units of 5 sessions can be delivered over a minimum of 5 calendar days and should be delivered within 12 calendar days. Thus, the entire acute treatment phase would normally take between 4 weeks to 11 weeks. At the end of each treatment block, study staff will enter progress notes for each participant in CPRS. These progress notes will be very brief in nature and contain no results or scores of assessments and will serve simply as records of treatment and assessment. The participant’s primary mental health provider will be listed as an additional signer on these

CSP #556 “The Effectiveness of rTMS in Depressed VA Patients”

Version 4.6, February 2016

Main Section of Protocol

notes. This is to ensure that providers are aware of the veterans progress throughout the study and to maintain an open line of communication with study staff.

Follow-up Phase. After the acute treatment phase ends, all patients will enter a 24 week follow-up period. Taper treatments are considered part of the Follow-up Phase. Follow-up visits will occur approximately monthly during the follow-up phase. These visits should be face-to-face but, in unusual circumstances, telephonic visits may be allowed. Appropriate assessments to measure treatment effects after the acute and follow-up phases will be collected as described in Table 2, Assessments and Frequencies of Administration, in Protocol section VI.G. At the end of each follow-up visit, study staff will enter progress notes for each participant in CPRS. These progress notes will be very brief in nature and contain no results or scores of assessments and serve simply as records of assessment. As on the notes in the acute phase, the participant's primary mental health provider will be listed as an additional signer on these notes.

F. Treatment Regimen

1. Rationale for Selection of rTMS Stimulation Parameters

The Planning Committee's decision regarding the choice of rTMS stimulation parameters in this trial was made in a systematic way with data from three sources.

- a. First, the Planning Committee members performed a thorough literature review of the rTMS antidepressant trials performed over the last 15 years (n=70 trials as of 12/06).

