This is an “intent-to-treat” protocol and any data of patients who are randomized to treatment will be retained for data analyses. As patients will remain under the care of their primary VA psychiatrist before, during and after participation in this study, the patient’s primary VA psychiatrist will remain central to the recruitment, participation and follow-up processes. Throughout a patient’s participation in the study, the site investigator will communicate with the patient’s primary VA psychiatrist to discuss the patient’s condition, reactions and any clinically significant adverse events. If a patient drops out or leaves the study for any reason or is suspended from the study for breaking study rules, every attempt will be made to contact the patient and complete a Termination Form.

J. Missed Visits and Study Termination

If a patient decides to withdraw their consent, a Termination Form will be completed. The Termination Form will include questions regarding the reason for termination and the patient's impression of the efficacy of the treatment to that point. If a patient is lost to follow-up or fails to come to clinic, the patient's primary VA psychiatrist will be informed.

The patient may be terminated from the study at any time if the SI deems that the patient has not been following the protocol. This will generally be done only when the protocol violation significantly increases the risk associated with continuing to participate in the study. A Termination Form will be completed. Patients who are terminated prior to the end of the acute treatment phase will be considered treatment failures.

Any female participant who becomes pregnant during the acute treatment phase of the study will discontinue the study treatments for safety reasons as the effects of rTMS on unborn fetuses is not known at this time and she will immediately enter the follow-up phase. Any female participant who gets pregnant during the follow-up phase of the study will continue to be followed-up in accordance with the protocol and complete all assessments. Women who become pregnant at any time during the study will be asked to sign a release of information in order for the study staff to access the medical records for the outcome of the pregnancy. Women who become pregnant during participation will be referred to an OB/GYN clinic.

K. Follow-up Procedures for Non-remitters and Non-responders

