Some secondary outcome measures, such as sustained response rate (“recovery”) and response on secondary outcome measures, can also be analyzed using logistic regression models. Other potential secondary analyses include continuous variables such as: change in suicidality, change in cognitive function and change in quality of life (QOL). The effect of rTMS on such continuous measures will be determined using random regression and similar techniques that maximize the use of available data in repeated measures designs.

Potential moderators of treatment response also will be analyzed using multivariate analysis of variance or regression techniques. In addition, exploratory analyses will be performed using signal detection techniques (Receiver Operator Characteristics or ROC) to attempt to identify novel moderators predictors of response. The following gives examples of some potential

analyses that may be carried out that use random regression techniques, which may be more sensitive to change than the logistic regression analyses.

a. Random regression approach to efficacy analyses

Random regression models will be used to test and evaluate treatment efficacy (see e.g., Gibbons et al., 1993). Such models trace the individual trajectories over time and, in effect, use available information to impute any missing data for comparable subjects. They thus compare the groups on a parameter describing the trajectory (e.g., the subject's response rate over time). This method not only minimizes loss of power and bias due to dropouts (for analytical purposes there are none), but also amplifies the reliability of measures using repeated measures per subject and thus usually increases power.

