If at any point someone presents for treatment and is visibly intoxicated, study staff will follow their local VA policy regarding the assessment of intoxication and behavior risk. From that point forward, the participant will be excluded from participation in the study and coded as a treatment failure.

To summarize, stopping criteria for treatment will include:

1. Alcohol use greater than one glass of wine/day or equivalent. Use of alcohol when patient has been warned of serious medication/alcohol interactions, will also fit this criteria. If patients are found to be noncompliant with this, the Site Investigator will decide whether to administer treatment and evaluate the patient's appropriateness for continued participation.
2. Abuse of illegal drugs. If patients are found to be noncompliant with this, the Site Investigator will decide whether to administer treatment and evaluate the

patient's appropriateness for continued participation. An exception to this will be patients who used marijuana up until the past 30 days. Ongoing THC abuse will change the status to "discontinued from the study".

3. Abuse or misuse of prescribed psychiatric medications will also result in either withdrawal from the study or inclusion as a noncompliant patient.

8. Special Procedures for Safety of Potentially Suicidal or Dangerous Patients

Appropriate and frequent assessment of suicidality is important when working with severely depressed individuals. Our approach to this is comprehensive in nature and includes multiple clinical interviews (CSSRS and HRSD) as well as self-report measures (BSS and BHS) that are given at baseline, weekly during acute treatment and the taper phases, and monthly during the follow-up phase. The following criteria will be used for the assessment of suicidality:

Baseline

- a) CSSRS: the endorsement of items 4 or 5, indicating Active Suicidal Ideation with Some Intent to Act, without Specific Plan or Active Suicidal Ideation with Specific Plan and Intent, OR the endorsement of an Actual Attempt, an Interrupted Attempt, an Aborted Attempt, or Preparatory Acts or Behaviors in the 6 months prior to assessment will trigger a clinical evaluation by the Site Investigator, the patient's primary mental health provider, or a mental health emergency clinician.

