If at any point during study participation, a participant has a seizure (not including syncope), that participant will be withdrawn from the study treatments immediately (they will still be followed for protocol assessments). All seizures (not including syncope) will be considered serious adverse events, and as such, will be reported to the DMC by the Clinical Research Pharmacist and Study Biostatistician. We will suspend enrollment if 10 participants experience a seizure (not including syncope) during study participation, and request that the DMC evaluate the SAE data, to determine if enrollment of new patients should be resumed without protocol changes, if protocol modifications should be made before resuming enrollment, or if the study should be terminated. In the event a patient on bupropion has a seizure associated with TMS treatment, enrollment and treatment of patients on any dose of bupropion will be suspended pending evaluation by the study Executive Committee and DMC as to (a) whether the event was a true seizure or merely syncope (b) whether the patient was receiving active treatment and (c) other circumstances that might have contributed to the seizure. Bupropion use could be reinstated if the Executive Committee, DMC, CIRB, and FDA agree that such action is appropriate. We recognize that study termination or modification based on serious adverse events, such as seizures, ultimately rests with the DMC and the study executive committee and that more stringent stopping points may be initiated during the study.

C. Training

Prior to the initiation of the study, a kick off meeting of the Study Group will be held. This meeting will include discussions of the study protocol, clinical and administrative details of the study, the roles/responsibilities of the SI and of the participating sites, assessment of workload, the informed consent process, regulatory issues and recruitment goals.

In conjunction with the kick-off meeting, training sessions will be held for the study staff. Training will include the correct use of all data collection forms, study definitions, recruitment strategies, and techniques of conducting patient assessments and rTMS treatment

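### The protocol gives two destinations, follow-up or study exit, for participants who leave acute treatment, which puts outcomes measured only at last session and week 24 at risk

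*Protocol*

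**What the plan says.** **Text that keeps the participant in follow-up**

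- VI.E, Acute Treatment Phase: "If a participant does not remit at the end of 30 sessions of treatment or drops out during treatment", the participant is a failure for the primary analysis and goes on to the 24-week follow-up, without a taper.
- VI.E, Follow-up Phase: "After the acute treatment phase ends, all patients will enter a 24 week follow-up period".
- VI.J: a participant who becomes pregnant during acute treatment stops treatment and moves straight to follow-up.
- X.B.9: after a seizure, "that participant will be withdrawn from the study treatments immediately (they will still be followed for protocol assessments".

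**Text that points to study exit**

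- VI.I: when a patient drops out, leaves for any reason or is suspended, "every attempt will be made to contact the patient and complete a Termination Form". No assessment is named. The same section says that data of randomized patients are retained for analysis.
- VI.J: withdrawal of consent and termination by the investigator each lead to a Termination Form. On coding, "Patients who are terminated prior to the end of the acute treatment phase will be considered treatment failures".
- Table 2, footnote 3: the form is for the end of the study or for earlier exit, and suspension is listed as one such exit.
- X.B.7: a visibly intoxicated participant is excluded from the study and coded a failure. Misuse of prescribed psychiatric medication (item 3) "will also result in either withdrawal from the study or inclusion as a noncompliant patient".

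**Analysis text**

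VIII.C.a says of random regression: "This method not only minimizes loss of power and bias due to dropouts (for analytical purposes there are none".

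**The concern.** VI.E and VI.I both speak of a patient who drops out, and VI.E and VI.J both code the patient a treatment failure, yet the destinations differ. Nowhere does the protocol separate stopping treatment from leaving the study. Two sites with the same kind of patient could act differently, and both could point to the text.

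What is at stake is data collection, which no analysis plan can repair afterwards. Quality of life and cognitive function are listed secondary outcomes (III.B), and PTSD symptoms are in secondary hypothesis 3. Their instruments have only two post-baseline time points. People who leave through dropout, non-adherence or return to substance use plausibly differ in outcome from those who stay. If their last-session and week-24 assessments are not done, these analyses drift towards an analysis of those who remained.

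**Working it through.** **1. The planned power, and whether this point touches it.** Inputs from VIII.A: 180 per group, 6% v 16%, stated power 81%. Two-sided alpha of 0.05 is assumed, since the sample-size text gives none. With a continuity-corrected pooled z test:

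- pooled rate 0.11; SE under the null = √(0.11 × 0.89 × 2/180) = 0.0330
- SE under the alternative = √((0.06 × 0.94 + 0.16 × 0.84)/180) = 0.0326
- power = Φ((0.10 − 1/180 − 1.96 × 0.0330)/0.0326) = 82.0%

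This agrees with 81% to about one point (86.1% without the correction). Dropouts already count as non-remitters, so neither the sample size nor this power changes.

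**2. The rules by reason for stopping in the acute phase**

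| Reason | Section | Primary coding | Later assessments |
|---|---|---|---|
| Drops out | VI.E | failure | 24-week follow-up |
| Drops out or is suspended | VI.I | not stated there | Termination Form; none named |
| Terminated by investigator | VI.J | failure | Termination Form; none named |
| Visibly intoxicated | X.B.7 | failure | excluded from study |
| Medication misuse | X.B.7 item 3 | depends on the choice | depends on the choice |
| Pregnancy | VI.J | not stated there | follow-up |
| Seizure | X.B.9 | not stated there | protocol assessments continue |

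The first two rows conflict directly. The payment example in VI.M leans towards exit: someone who terminates in treatment week 3 receives payments 1 and 2, but not payment 3, which is for follow-up visits.

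**3. Which outcomes are exposed (Table 2)**

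- HRSD, MADRS, BDI and BSS are scheduled after every five-session block, so an early leaver may already have post-baseline values.
- VR-36, the neuropsychological battery, CAPS and PCL are scheduled at baseline, in the 30/last column and at week 24. A participant who exits mid-phase without the 30/last visit has a baseline value only.
- The longer-term model in VIII.C.a uses follow-up weeks 4 to 24. A participant who exits in the acute phase contributes nothing to it for any measure.

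A baseline value alone carries no information on that person's change. The model then relies on the missing-at-random assumption, with no later observation of that participant to support it.

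**4. How many participants.** The protocol plans no dropout rate. Assuming 5% to 20%:

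- 360 × 0.05 = 18
- 360 × 0.20 = 72

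These are upper bounds. They include consent withdrawals and losses to contact, and some leavers would still complete a last assessment.

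**5. Illustrative precision cost.** For an assumed standardized difference of 0.3 and two-sided alpha of 0.05, power = Φ(0.3 × √(n/2) − 1.96):

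- n = 180 per arm: 81.2%
- n = 171 (5% lost): 79.2%
- n = 144 (20% lost): 72.1%

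Bias cannot be computed: the protocol gives neither a dropout rate by arm nor standard deviations for these outcomes.

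**6. The choice in X.B.7 item 3.** Withdrawal before the end of the acute phase is a failure under VI.J; staying in leaves the HRSD to decide. The choice alters the primary count only if the participant would have remitted. At the planned rates that is 10 × 0.06 = 0.6 to 10 × 0.16 = 1.6 per 10 such participants.

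**The case against.** The strongest reply is that the texts can be read together: VI.E governs people who stop treatment, while VI.I and VI.J govern people who leave the study, as footnote 3 suggests. VI.I does not forbid assessments, the 30/last column can cover an early last session, and VI.J says investigator termination is generally reserved for violations that significantly raise the risk of continuing. This stands to the extent that loss of data is a risk under one reading, not a stated rule. It does not remove the conflict, because VI.E itself uses the dropout wording. Where the protocol expressly wants data after a medical stop, it says so.

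A reader might also infer more than the documents support:

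- *All secondary outcomes are lost.* MADRS, BSS and BDI are measured after every block.
- *Sustained remission, and the cost per sustained remission, are distorted.* Secondary hypothesis 1 concerns remitters, and acute-phase dropouts are failures.
- *Medical stops keep their data and non-adherence stops lose theirs.* X.B.8 words non-compliance with the safety plan, and onset of mania, as stopping study treatments.
- *The analysis section denies that anyone drops out.* VIII.A and VIII.B.2 name dropouts and code them. The parenthesis describes how random regression uses partial records.
- *About 43 of 360 participants would be lost, and more on active treatment.* The 43 borrows the NIH trial's 88% retention (360 × 0.12) and counts people whom no rule could retain. Section I.E cites site discomfort of 18% v 10%, but also says that pain rarely caused dropout in that trial (two to three patients).

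**Conclusion.** The concern holds in a limited form. VI.E conflicts with VI.I, and VI.J and X.B.7 add further exits with no assessments named; these sections must be reconciled. Primary remission is largely protected by failure coding, with a small opening at X.B.7 item 3, and sustained remission as worded is unaffected by acute dropouts.

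The real exposure is to the VR-36, neuropsychological battery, CAPS and PCL, and to the follow-up-phase models. For those measures the remark that there are analytically no dropouts is too strong. The size is unknown: 18 to 72 of 360 is an upper bound that rests on an assumed 5% to 20% leaving, and the direction of any bias cannot be stated. It is worth correcting because the remedy is cheap and data that are not collected cannot be recovered.

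**What to change.** Reconcile VI.E, VI.I, VI.J and X.B.7 so that stopping study treatment and leaving the study are separate events.

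- A participant whose treatment stops is asked to complete the existing 30/last assessments and then the scheduled follow-up visits, by telephone in unusual circumstances as VI.E allows. This extends what is already written for pregnancy and seizure.
- The Termination Form alone is used when consent is withdrawn, contact is lost, or there is a documented safety reason why assessments cannot continue.
- X.B.7 item 3 gets one outcome-coding rule and one data-collection rule.
- The parenthesis in VIII.C.a is deleted or qualified.

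None of this changes when treatment is stopped, the sample size, the planned power or the instruments. The cost is a wording amendment, a clarification to sites, and existing visits carried out for some additional participants.

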***B= Baseline**

***S= Screening**

¹ Sessions 21-25 and 26-30 may not be required if patient goes into remission earlier

² Must be conducted within 7 days prior to randomization

³ Termination Form will be completed at the end of the study OR when a patient decides to end study participation prior to the study completion date; i.e., a patient decides to withdraw or leave the study for any reason, withdraws consent, or is suspended from the study.

1. Demographics, Medical History, Physical Exam, Laboratory, Toxicology, Pregnancy

Test and Medication Use. Relevant demographics will be collected as to age, gender, racial/ethnic grouping, military history and income. In addition, a standard Medical History and Physical Exam will be completed as well as laboratory tests including a Complete Blood Count (CBC), electrolytes (chemistry), thyroid panel and a liver function test. An alcohol test and urine drug toxicology screen will be conducted prior to randomization and also randomly during the following time points of study participation:

- Acute Treatment Phase: 2nd, 4th, and 6th (if still in acute treatment) weeks
- Taper Phase: 2nd week
- Follow-up Phase: 1st, 3rd, and 5th months

A pregnancy test will be conducted on all female patients of childbearing potential (that is, all women except for those who are post menopause for > 2 years or who have a history of hysterectomy or surgical sterilization) prior to randomization and every four weeks during the study. Information on medication use (prescription, natural food products, and “over the counter”) will be collected at screening and updated after each block of five sessions during the treatment phase and every four weeks during the follow-up phase.

2. Structured Clinical Interview for DSM-IV (SCID) (First et al., 2002). The Structured Clinical Interview for DSM-IV Axis I Disorders (SCID) is a semi-structured interview that is used to make the major DSM-IV Axis I diagnoses in the most uniform manner possible.

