17. Beck Hopelessness Scale (BHS) (Beck et al., 1974). The Beck Hopelessness Scale is a self-report measure consisting of 20 “yes/no” items. A total severity of hopelessness is calculated from summing the 20 items and guidelines for interpretation for scores are as follows: 0-3 = minimal hopelessness; 4-8 = mild hopelessness; 9-14 = moderate hopelessness; and 15-20 = severe hopelessness. The BHS will be given at screening, weekly during acute treatment and taper phases and then monthly during the follow-up phase.

18. Beck Scale for Suicide Ideation (BSS). To help clinicians screen psychiatric patients for suicidal ideation, the Beck Scale for Suicide Ideation (Beck and Steer, 1991) was developed, and is herein referred to as the BSS. This self-report measure consists of 21 items and is one of the most thorough assessments of both active and passive suicidal ideation. Respondents are asked to rate the severity of each item on a 3-point scale with scores ranging from 0 to 2. The first five items on the BSS are regarded as a screener for suicidal ideation and assess one's desire to live, desire to die, reasons to live and reasons to die, and suicidal ideation. The remainder of the BSS assesses the duration and frequency of suicidal ideation, ambivalence regarding suicidal ideation, reasons for living / deterrents for suicide, suicide plan / opportunity to enact plan, expectations for following through after an attempt, preparations that have been made to ready for a suicide, past suicide attempts, and wish to die during past suicide attempts. It should be noted that the psychiatrist responsible for the assessment of the patient is responsible for performing a more detailed assessment of any patient showing an increase in BSS score. The BSS will be given at screening, weekly during acute treatment and taper phases and then monthly during the follow-up phase.

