Throughout the study, site staff will also monitor participants' use of substances including alcohol, OTC medication, opiates, and street drugs for possible abuse through the use of self-report measures. Prior to each treatment session, study staff will ask participants if they have used any substances in the past 24 hours and if so, how much was used. Study staff will further monitor participants' alcohol and other substance use with weekly administrations of the Alcohol / Drug of Choice Timeline Followback Method (TLFB) (Sobell and Sobell, 1992) during the acute and taper phases of treatment, and monthly administrations of the TLFB during the follow-up phase. The TLFB is a self-report measure of recent drinking behavior or substance abuse. Using a calendar, the patients will retrospectively estimate their daily consumption of alcohol and other substances over the past 7 days prior to the interview. This will enable the study staff to quantify the amount of substances patients are using, therefore tracking changes in

these amounts and addressing problematic substance use at the earliest possible instance. This tool is used for monitoring purposes during the study, not for enrollment.

Participants will also complete the MAST and DAST during screening, at the end of acute treatment, and at the end of the follow-up phase.

Use of substances is not prohibited during study participation; however, participants are discouraged from consuming more than one alcoholic drink per day during their participation. If it is determined that a participant is abusing substances, study staff will alert the SI. At that time, the SI will evaluate the situation and determine if it is appropriate for the participant to continue. The Site PI will use the “VA/DoD Clinical Practice Guideline for Management of Substance Use Disorders” (The Management of Substance Use Disorders Working Group, 2009) as a reference in the evaluation of the situation.

Additionally, during the informed consent process, participants must agree to allow study staff to contact their primary mental health provider should the participant begin to abuse substances during the course of their participation in the treatment trial. Potential participants that do not agree to this portion of the informed consent will not be allowed to enroll.

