- b) HRSD: a score of 2 or greater on items 10 (Anxiety-Psychic) or 11 (Anxiety-Somatic) or a score of 4 on item 9 (Agitation) IN combination with a score of 3 or greater on item 3 (Suicide) will trigger a clinical evaluation by the Site Investigator, the patient's primary mental health provider, or a mental health emergency clinician.
- c) MADRS: A score of 4 or greater on item 10 (Suicide Intent) of the MADRS will trigger a clinical evaluation by the Site Investigator, the patient's primary mental health provider, or a mental health emergency clinician.

- d) BSS: any positive response to an item on the BSS could indicate suicidal ideation thus triggering a clinical evaluation by the Site Investigator, the patient's primary mental health provider, or a mental health emergency clinician.
- e) BHS: A score of 9 or greater indicating moderate hopelessness on the BHS will trigger a clinical evaluation by the Site Investigator, the patient's primary mental health provider, or a mental health emergency clinician.
- f) STAXI-2: Scores above the 75th percentile or below the 25th percentile on the STAXI-2 will trigger an assessment of danger to self or danger to others.

Acute Treatment and Taper Phases

- a) CSSRS: the endorsement of items 4 or 5, indicating Active Suicidal Ideation with Some Intent to Act, without Specific Plan or Active Suicidal Ideation with Specific Plan and Intent, OR the endorsement of an Actual Attempt, an Interrupted Attempt, an Aborted Attempt, or Preparatory Acts or Behaviors since the last assessment will trigger a clinical evaluation by the Site Investigator, the patient's primary mental health provider, or a mental health emergency clinician.
- b) HRSD: a score of 2 or greater on items 10 (Anxiety-Psychic) or 11 (Anxiety-Somatic) or a score of 4 on item 9 (Agitation) IN combination with a score of 3 or greater on item 3 (Suicide) will trigger a clinical evaluation by the Site Investigator, the patient's primary mental health provider, or a mental health emergency clinician.
- c) MADRS: A score of 4 or greater on item 10 (Suicide Intent) of the MADRS will trigger a clinical evaluation by the Site Investigator, the patient's primary mental health provider, or a mental health emergency clinician.
- d) BSS: any positive response to an item on the BSS could indicate suicidal ideation thus triggering a clinical evaluation by the Site Investigator, the patient's primary mental health provider, or a mental health emergency clinician.

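### The pregnancy rule in VI.J stops study treatments only for conception in the acute phase, so it has no stop for a remitter who conceives during the taper (minor safety wording)

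*Protocol*

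**What the plan says.** Section VI.J (Missed Visits and Study Termination) has two pregnancy rules, each tied to a phase.

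- **Acute treatment phase.** A participant who "becomes pregnant during the acute treatment phase of the study will discontinue the study treatments for safety reasons". The reason given is that the effects of rTMS on a fetus are not known. She then moves straight into follow-up.
- **Follow-up phase.** A participant "who gets pregnant during the follow-up phase of the study will continue to be followed-up in accordance with the protocol and complete all assessments". Nothing is said about study treatments.

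Section VI.E (Intervention Procedure) gives further stimulation to those who remit: "The taper will include 3 treatment sessions in the first week, 2 in the second week and 1 in the last week of the taper". The same section states where this belongs: "Taper treatments are considered part of the Follow-up Phase".

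Section VI.G.1 schedules a pregnancy test before randomization and every four weeks during the study for women of childbearing potential. It does not say what follows from a positive result.

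**The concern.** A follow-up rule without a treatment stop would be harmless if follow-up contained no stimulation. Here it contains up to six sessions for every remitter. The only reason given for stopping is unknown fetal risk from rTMS, and that holds for a taper session as much as for an acute one. The rule is therefore narrower than its own reason. A site that follows VI.J and VI.E to the letter finds no instruction to cancel the remaining taper sessions of a woman who conceives during taper.

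What is at stake is the clarity of a participant-safety rule across nine sites. Efficacy is not involved.

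**Working it through.** **Text check**

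| Situation | Sentence of VI.J that applies | Stop of study treatments? |
|---|---|---|
| Conceives in acute phase | First | Yes |
| Conceived in acute phase, test positive in taper | First, since it turns on when she becomes pregnant | Yes, though staff must date the conception |
| Conceives in taper | Second, since VI.E puts taper in follow-up | None stated |
| Conceives after taper | Second | Not needed, no stimulation remains |

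Only the third row is a gap. The other places where a stop might appear do not close it:

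- Exclusion criterion 1 and inclusion criterion 10 act at entry.
- The stopping rules for substance use (X.B.7), suicidality, firearms and mania (X.B.8) and seizure (X.B.9) do not mention pregnancy.
- The rest of VI.J on pregnancy deals with release of records and obstetric referral.

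**Size**

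The plan gives no figure to reproduce. Inputs from the protocol are 180 participants per arm and 16% planned active remission (VIII.A), taper sessions of 3 + 2 + 1 = 6 in 21 days (VI.E), and a test every 28 days (VI.G.1). The rest is assumed: 5% to 20% of remitters are women of childbearing potential, 2% to 10% become pregnant per year, and a lag L of 10 to 14 days separates conception from a positive test.

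1. Active remitters: 0.16 × 180 = 28.8.
2. Conceptions in active taper:
   - low: 28.8 × 0.05 × 0.02 × 21/365 = 0.0017
   - high: 28.8 × 0.20 × 0.10 × 21/365 = 0.033
3. Share detectable before taper ends, with conception uniform over the 21 days, is (21 − L)/21. This is 0.333 at L = 14 and 0.524 at L = 10. Expected detectable cases: 0.0017 × 0.333 = 0.0006 to 0.033 × 0.524 = 0.017.
4. Share detected by the four-weekly test alone, at a random point in its cycle, is (21 − L)²/(2 × 28 × 21). This is 49/1176 = 0.042 at L = 14 and 121/1176 = 0.103 at L = 10. Expected cases: 0.0017 × 0.042 = 0.00007 to 0.033 × 0.103 = 0.0034.
5. Sessions a stop could still prevent, taking the earliest case of conception on taper day 0: at L = 14 only the single week-3 session remains. At L = 10, 1 to 3 sessions remain, depending on the days of the two week-2 sessions. Later conceptions leave fewer.

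**The case against.** The strongest reply is that this is silence and does no harm. The follow-up sentence concerns observation and does not order stimulation. Pregnancy is an entry exclusion, contraception is required, tests recur every four weeks, and the stated reason for stopping is not limited to a phase. Any sensible clinician would cancel the remaining sessions. The consent pages are also not available to read and may carry the instruction.

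Most of this is fair, and it keeps the point small. It does not remove it. The sponsor chose to write a stopping rule and wrote it for only one of the two periods in which stimulation is given. The follow-up sentence refers staff back to a protocol whose follow-up phase includes taper. Consent wording, whatever it says, would not correct VI.J. The seizure rule in X.B.9 shows the simpler form: it withdraws the participant from study treatments at any point and keeps the assessments. That is a drafting model and does not contradict VI.J.

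Four stronger readings are tempting, and the protocol does not support them:

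- *Any pregnant participant could go on to receive taper.* Conception in the acute phase already ends the study treatments.
- *The protocol authorises stimulation in pregnancy.* It says nothing either way.
- *The protocol has two competing definitions of follow-up, and neither pregnancy rule covers taper.* Some schedules do name taper apart from follow-up, for example "weekly during acute treatment and taper phases and then monthly during the follow-up phase" in VI.G and the heading "Acute Treatment and Taper Phases" in X.B.8. These are labels for assessment frequency. VI.E contains an explicit definition, and VI.D lists only screening, acute treatment and a 24-week follow-up. The point rests on VI.E and VI.J alone.
- *Six sessions of exposure are at issue.* No rule can act before detection, so 1 to 3 sessions is the most that could be prevented under the lags assumed here.

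**Conclusion.** The concern holds as a minor wording gap. Under VI.J read with VI.E, a remitter who conceives during the three-week taper is subject to no stated stop of study treatments, although the reason given for the acute-phase stop applies to her as well.

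Across the trial, about 0.002 to 0.03 such conceptions are expected in the active arm, of which about 0.0006 to 0.017 could be detected while sessions remain. These figures rest on assumed shares of women, pregnancy rates and detection lags that the protocol does not give. The ranges are wide, but every value is close to zero. The primary analysis is untouched, since remission is determined at the end of acute treatment and taper follows it. The finding is limited to the protocol text available for review.

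**What to change.** Replace the phase-specific pair of sentences in VI.J with one rule: any participant who becomes pregnant, or is found to be pregnant, at any time while study treatments (including taper) are being given discontinues all study treatments and continues all follow-up assessments. Including pregnancies that are found during treatment spares staff from dating conception when a test is positive in taper. The rule should apply to both arms so that the blind is kept.

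The cost is one sentence in an amendment or memo of clarification, with no extra visits, tests or participants.
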